6.2.15 Visit 7 (Week 36)

Note: Confirm the arrangement for laboratory sample pick-up on the day of the Week 36 Visit with the courier (see Central Laboratory Procedures Manual).

1. For all applicable patients: Verify continuation of (or any change to) contraceptive method since previous visit and document.
2. Obtain samples for the following laboratory tests, and record the date and time of collection:

- a. Hematology and chemistry (including liver function tests).
 - b. TSH, free T3, and free T4.
 - c. Urine sample for urinalysis.
 - d. For females of childbearing potential: urine pregnancy test.
Note: For processing, labeling and shipping of samples, follow the instructions provided in the Central Laboratory Procedures Manual.
3. Assess AEs by asking open-ended queries and record the assessments.
 4. Record concomitant medication use; assess and record any changes to anti-PD medication dose or regimen.
 5. Obtain and record BP and pulse measurements after at least 5 minutes supine rest and again after standing for approximately 1 and 3 minutes.
 6. Obtain 12-lead ECG. Ensure the ECG is collected when the patient is not experiencing dyskinesia that would interfere with an adequate recording. Assess any changes from Baseline for clinical significance.
 7. Record the date and approximate time of the most recent dose of levodopa taken prior to the UPDRS assessment.
 8. Perform the following assessments in the ON state:
 - a. Perform full UPDRS Parts I, II, III (motor) and IV. UPDRS Part III should be performed approximately 1 to 3 hours after the patient has taken a scheduled dose of levodopa (preferably their morning dose of levodopa). UPDRS in the ON state will be measured at a time representative of the ON state in that patient, not in “best” ON.
 - b. Administer the following assessments:
 - CGI-I.
 - PGI-I.
 - c. Have the patient complete the following self-assessment questionnaire:
 - ESS.
 9. Administer the following assessments (may be done anytime during visit):
 - a. mMIDI. (Note: After Baseline, if patient has one or more positive modules on the mMIDI, their continued participation in the study should be discussed with the Medical Monitor.)
 - b. C-SSRS.
 - c. Assessment for episodes of sudden onset of sleep.
 - d. Healthcare Resource Utilization.
 10. Perform physical and neurological examination, and assess any changes from Baseline for clinical significance.
 11. Collect the unopened and opened IMP bottles dispensed at the Week 24 visit.
 12. Assess and document IMP accountability and compliance (document any missed dose(s), lost tablets and number of tablets taken).
 - a. Review and reconcile any discrepancies with the patient.

13. Dispense open-label IMP (bottles) based on the dosage (60 mg BID or 120 mg BID) as determined by the investigator.
 - a. Record the date IMP was dispensed in IMP dispensing records.
14. Review the dosing instructions for open-label IMP with the patient, answer any questions, and remind the patient to return unopened and opened IMP bottles at the next visit.
 - a. Ensure that the patient understood the dosing instructions and the use of extra doses included in the bottle if visit delayed and/or use of visit window.
15. Schedule the Week 44 Visit. If needed, use the visit window in relation to the date of the Baseline visit.

6.2.16 Visit 7.5 (Week 44)

Note: Confirm the arrangement for laboratory sample pick-up on the day of the Week 48 visit with the courier (see Central Laboratory Procedures Manual).

1. Obtain hematology sample and record the date and time of collection. For processing, labeling and shipping of sample, follow the instructions provided in the Central Laboratory Procedures Manual.
2. Instruct the patient to complete the PD diary on the 3 consecutive days (i.e., 3 consecutive 24-hour periods) directly preceding the Week 52 visit. Provide the patient with the PD diary.
3. Schedule the next study visit (Week 52). If needed, use the visit window in relation to the date of the Baseline visit.

6.2.17 Telephone Call on Week 52 (to Occur Prior to PD Diary Start Date)

Patients will be telephoned prior to the start of the 3-day PD diary completion period preceding the Week 52 visit.

Note: The telephone call should take into account the window for study visits to ensure the call is made, at the latest, on the day prior to the start of the PD diary completion period.

1. Patients will be reminded of the following:
 - a. To comply with instructions for taking the IMP.
 - b. To complete the PD diary according to the instructions (see [Section 7.1](#)). The patients will be reminded by the trainer/rater to apply the ON and OFF definitions during PD diary completion on the 3 consecutive days (i.e., 3 consecutive, 24-hour periods) directly preceding the scheduled Week 52 visit. Any questions from the patient regarding PD diary completion will be addressed.
 - c. To bring the PD diary with them to the visit.
 - d. To bring the IMP with them to the visit.
 - e. To take the IMP in the morning before the visit.

- f. To take all doses of their routine medications (including anti-PD medications) according to their normal schedule on the day of the scheduled visit and to bring their medications to the visit.

6.2.18 Visit 8 (Week 52)

Note: Confirm the arrangement for laboratory sample pick-up on the day of the Week 52 Visit with the courier (see Central Laboratory Procedures Manual).

1. For all applicable patients: Verify continuation of (or any change to) contraceptive method since previous visit and document.
2. Obtain samples for the following laboratory tests, and record the date and time of collection:
 - a. Hematology and chemistry (including liver function tests).
 - b. TSH, free T3, and free T4.
 - c. Urine sample for urinalysis.
 - d. For females of childbearing potential: urine pregnancy test.

Note: For processing, labeling and shipping of samples, follow the instructions provided in the Central Laboratory Procedures Manual.
3. Review the patient's PD diary recordings for the 3 consecutive days (i.e., 3 consecutive 24-hour periods) directly preceding this visit, and address any illegible or unclear entries.
4. Assess AEs by asking open-ended queries and record the assessments.
5. Record concomitant medication use; assess and record any changes to anti-PD medication dose or regimen.
6. Obtain and record BP and pulse measurements after at least 5 minutes supine rest and again after standing for approximately 1 and 3 minutes.
7. Obtain 12-lead ECG. Ensure the ECG is collected when the patient is not experiencing dyskinesia that would interfere with an adequate recording. Assess any changes from Baseline for clinical significance.
8. Obtain weight.
9. Record the date and approximate time of the most recent dose of levodopa taken prior to the UPDRS assessment.
10. Perform the following assessments in the ON state:
 - a. Perform full UPDRS Parts I, II, III (motor) and IV. UPDRS Part III should be performed approximately 1 to 3 hours after the patient has taken a scheduled dose of levodopa (preferably their morning dose of levodopa). UPDRS in the ON state will be measured at a time representative of the ON state in that patient, not in "best" ON.
 - b. Administer the following assessments:
 - CGI-I.
 - PGI-I.
 - PDQ-39.

- EQ-5D-5L.
 - Non-motor Symptom Assessment Scale.
- c. Have the patient complete the following self-assessment questionnaire:
- ESS.
11. Administer the following assessments (may be done anytime during visit):
- a. mMIDI. (Note: After Baseline, if patient has one or more positive modules on the mMIDI, their continued participation in the study should be discussed with the Medical Monitor.)
 - b. C-SSRS.
 - c. Fall questionnaire.
 - d. Assessment for episodes of sudden onset of sleep.
 - e. Healthcare Resource Utilization.
12. Perform physical and neurological examination, and assess any changes from Baseline for clinical significance.
13. Collect the unopened and opened IMP bottles dispensed at the Week 36 Visit.
14. Assess and document IMP accountability and compliance (document any missed dose(s), lost tablets and number of tablets taken).
- a. Review and reconcile any discrepancies with the patient.
15. Schedule the Safety Follow-Up Visit (Week 56). If needed, use the visit window in relation to the date of the Baseline visit.

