Patients who return valid practice PD diaries and who the investigator considers eligible for the study will have the Baseline Visit scheduled within 6 weeks from the Screening Visit. They will be instructed to complete the Baseline PD diary on the 3 consecutive days directly preceding the scheduled Baseline Visit. The trainer/rater will telephone the patient prior to the start date to remind them to start keeping the PD diary, to review the ON and OFF definitions, and to answer any questions the patients or caregiver may have regarding completion instructions. The patients will be requested to bring the Baseline PD diary to the Baseline Visit, at which the PD diary will be assessed for validity and to confirm the patient's eligibility. Patients not meeting the criteria for valid Baseline PD diary completion may be retrained, as described above, and may return for another Baseline assessment within the 6 week Screening Period.

Eligible patients who meet all the entry criteria at Baseline will be enrolled

PROTOCOL SYNOPSIS

	
and receive open-label IMP for 52 weeks. Patients will be assessed for safety and tolerability regularly throughout the study and 4 weeks after their last dose of IMP. Blood pressure and pulse (supine and standing) will be taken at each outpatient visit.
 
For scheduled study visits at Weeks 2, 6, 12, 24, 36, and 52, patients will be instructed to have already taken their normally scheduled dose of levodopa and their IMP prior to arriving at the study site in order to have their UPDRS Part III evaluated in ON (within approximately 1 to 3 hours after taking their levodopa dose). UPDRS in OFF will not be evaluated. Patients will be asked to complete a PD diary on the 3 consecutive days directly preceding visits at Weeks 12, 24 and 52. Prior to each 3-day PD diary completion period, patients will be telephoned to be reminded to comply with the PD diary instructions. Patients will be requested to bring their PD diary to the scheduled visits.
 
Please refer to the Schedule of Events/Evaluations (Table 1) for specific timing of assessments.

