
Data and Safety Monitoring
	
Concurrent safety monitoring is planned for this study. Responsibility for safety monitoring will be assigned to the independent Data and Safety Monitoring Board (DSMB) of study TOZ-CL05, which will also oversee the safety of TOZ-CL06 by reviewing relevant data on a regular basis. The DSMB will consist of members who are independent from Biotie Therapies, Inc. Study enrollment will not be halted during planned DSMB reviews of safety data. The objectives and procedures for the DSMB are detailed in the DSMB charter.

Statistical Analysis
	
Safety data, including TEAEs, vital signs, ECGs, ESS, physical examination, and clinical laboratory test results will be summarized descriptively. The descriptive statistics will be provided for the observed data and for the change from Baseline at each measured time point, where appropriate. Tables will summarize TEAE data as appropriate. Note that counting will be by patient, not event and patients will only be counted once within each system organ class or preferred term.
 
Laboratory test results will be classified as below the lower limit of normal, within normal limits, and above the ULN. Shift tables will be used to summarize changes from Baseline to each visit by treatment group.
 
Clinically significant physical or neurological exam findings and any clinically significant out-of-range laboratory tests that are TEAE will be recorded as TEAEs and documented in the TEAE summaries.
 
Other variables will be summarized descriptively. Descriptive statistics will be generated for the observed and the change from Baseline. For categorical variables, frequency and percentages will be produced.

Table 1: Schedule of Events/Evaluations

Study Period	Screening ^a	Baseline Predose	Open-Label Treatment (52 weeks)						Safety Follow-Up	Early Termination ^w	Unscheduled
	Study Week ^b	BL	2 (± 3 d)	6 (± 3 d)	12 (± 3 d)	24 (± 7 d)	36 (± 7 d)	52 (± 14 d) [16 weeks]	56 (28 ± 3 d after last dose of IMP)		
Study Visit	V1	V2	V3	V4	V5	V6	V7	V8	V9		
Written Informed Consent	X										
Demographics and Medical History, including neurological and PD history	X										
Recording of concomitant and anti-PD medications	X	X	X	X	X	X	X	X	X	X	X
BP ^c , pulse ^c	X ^d	X ^d	X	X	X	X	X	X	X	X	X ^e
12-lead ECG ^f	X	X ^g	X	X	X	X	X	X	X	X	X ^e
Weight (include height at Screening)	X				X	X		X	X	X	X ^e
Physical and neurological examination	X				X	X	X	X	X	X	X ^e

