- ^b Visit windows for scheduled visits after Baseline (V2) are in relation to the date of the Baseline Visit (V2).
- ^c Obtain and record BP and pulse measurements after at least 5 minutes supine rest and again after standing for approximately 1 minute and 3 minutes.
- ^d At Screening and Baseline (before dosing), obtain and record serial BP and pulse measurements after at least 5 minutes supine rest and again after standing for approximately 1 and 3 minutes. Repeat these BP and pulse measurements 2 more times approximately 10 minutes apart.
- ^e Optional activities (e.g., additional assessments for evaluation of AEs) that may be performed at the investigator’s discretion.
- ^f A resting supine 12-lead ECG will be collected after the patient has been in a supine position for a minimum of 5 minutes. Ensure the ECG is collected when the patient is not experiencing dyskinesia that would interfere with an adequate recording.
- ^g At Baseline, obtain three 12-lead ECGs (i.e., 3 serial readings, performed several minutes apart). Ensure the ECGs are collected when the patient is not experiencing dyskinesia that would interfere with an adequate recording.
- ^h To be collected during patient’s ON state.
- ⁱ UPDRS to be measured in ON state. UPDRS Part III should be measured approximately 1 to 3 hours after patients have taken a scheduled dose of levodopa (preferably their morning dose of levodopa). Patients will be instructed to have already taken their normally scheduled dose of levodopa and their IMP before arriving at the study site in order to have their UPDRS Part III evaluated in the ON state. UPDRS in the ON state will be measured at a time representative of the ON state in that patient, not in the patient’s “best” ON.

Table 1: Schedule of Events/Evaluations (continued)

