3.0 STUDY DESIGN

3.1 Study Description

This is a Phase 3, international, multicenter, open-label study in levodopa-treated patients with PD experiencing end-of-dose "wearing-off". This study includes a Screening Period of up to 6 weeks that starts with a Screening Visit, followed by a 52-week Open-Label Treatment Period and a Safety Follow-Up Visit 4 weeks after completion of investigational treatment. After providing written informed consent, patients will undergo screening evaluations. Patients must meet all inclusion criteria and none of the exclusion criteria and they must successfully complete the diary training and achieve 80% overall diary concordance with the PD diary trainer/rater including at least 1 OFF interval to be considered for randomization. If preliminary eligibility is confirmed by the investigator, patients will then be scheduled for a Baseline Visit and will be required to return a valid set of Baseline diaries. Final eligibility will be determined at the Baseline Visit.

Patients will return to the study site for evaluation at scheduled visits at Weeks 2, 6, 12, 24, 36 and 52. Patients will be contacted by telephone before the start of each 3-day PD diary completion period to be reminded to complete the diary. **Patients will also be scheduled for a laboratory draw (hematology measurement only) at Weeks 4, 8, 10, 16, 20 and 44.** A final Safety Follow-Up Visit (Week 56) will occur 28 ± 3 days after the patient's last open-label dose of tozadenant. Upon starting study treatment, patients will receive open-label tozadenant at a dose of 120 mg BID. Adjustments to the open-label tozadenant dose are allowed to be made by the investigator starting at Week 2 and at any of the subsequent visits. Doses of 60 or 120 mg

BID are permitted; the investigator may adjust a patient's dose to either level as clinically indicated. The Interactive Response System (IXRS) will be used to assign, track and manage the tozadenant inventory at each study site.

Patients' concomitant anti-PD medications may be adjusted as needed under the investigator's supervision (see [Section 5.9.1](#)). The optimal dose of open-label tozadenant for each patient will be defined following discussion between the patient and the investigator, taking into account the potential for improvement of disease symptoms and the tolerability profile.

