period, patients will be telephoned to be reminded to comply with the PD diary instructions. Patients will be requested to bring their PD diary to the scheduled visits. Safety evaluations will be performed at each study visit. At specified visits, patients will be asked to return their IMP dispensed at the previous visit (including all unopened and opened IMP bottles) and to bring their other medications to the visit. Patients will be instructed to have already taken their normally scheduled dose of levodopa and their IMP prior to arriving at the study site in order to have their UPDRS Part III evaluated in the ON state (within approximately 1 to 3 hours after taking their levodopa dose). UPDRS in OFF will not be evaluated. Pharmacokinetic (PK) blood samples will be collected for tozadenant at Week 2 as outlined in [Table 1](#), Schedule of Events/Evaluations. **Patients will also be scheduled for a laboratory draw (hematology measurement only) at Weeks 4, 8, 10, 16, 20 and 44 as outlined in [Table 1.1](#).** All patients completing the study will be scheduled for a required postdose Safety Follow-Up Visit 28 ± 3 days after completion of the 52-week open-label treatment period. In the event of Early Termination, patients will be asked to complete an Early Termination Visit as soon as possible and to return for a Safety Follow-Up Visit 28 ± 3 days after their last dose of IMP, unless the Early Termination Visit itself occurred 28 or more days after the last dose of IMP.

Please refer to the Schedule of Events/Evaluations in [Table 1](#) and [Table 1.1](#) for specific timing of assessments and [Section 6.2](#) for detailed study procedures.

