6.2.19 Safety Follow-Up Visit (Visit 9, Week 56)

Note: Confirm the arrangement for laboratory sample pick-up on the day of the Safety Follow-Up Visit (Week 56) with the courier (see Central Laboratory Procedures Manual).

All patients who complete dosing and study evaluations through Week 52 will be scheduled for a required Safety Follow-Up Visit at Week 56. If a patient took the last dose of IMP less than 28 days prior to the Early Termination Visit, a Safety Follow-Up Visit is required.

1. For all applicable patients: Verify continuation of (or any change to) contraceptive method since previous visit and document.
2. Obtain samples for the following laboratory tests, and record the date and time of collection:
 - a. Hematology and chemistry (including liver function tests).
 - b. TSH, free T3, and free T4.
 - c. Urine sample for urinalysis.
 - d. For females of childbearing potential: urine pregnancy test.

Note: For processing, labeling and shipping of samples, follow the instructions provided in the Central Laboratory Procedures Manual.
3. Assess AEs by asking open-ended queries and record the assessments.

4. Record concomitant medication use; assess and record any changes to anti-PD medication dose or regimen.
5. Obtain and record BP and pulse measurements after at least 5 minutes supine rest and again after standing for approximately 1 and 3 minutes.
6. Obtain 12-lead ECG. Ensure the ECG is collected when the patient is not experiencing dyskinesia that would interfere with an adequate recording. Assess any changes from Baseline for clinical significance.
7. Obtain weight.
8. Perform physical and neurological examination and assess any changes from Baseline for clinical significance.
9. Have the patient complete the following self-assessment questionnaire (to be collected during patient's ON state):
 - a. ESS.
10. Administer the following assessments (may be done anytime during visit):
 - a. mMIDI.
 - b. C-SSRS.
 - c. Assessment for episodes of sudden onset of sleep.

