3. STUDY DESIGN

This is a Phase 3, international, multicenter, open-label study in levodopa-treated patients with PD experiencing end-of-dose “wearing-off”. This study includes a Screening Period of up to 6 weeks that starts with a Screening Visit, followed by a 52-week Open-Label Treatment Period and a Safety Follow-Up Visit 4 weeks after completion of investigational treatment. After providing written informed consent, patients will undergo screening evaluations. Patients must meet all inclusion criteria and none of the exclusion criteria and they must successfully complete the diary training and achieve 80% overall diary concordance with the PD diary trainer/rater including at least 1 OFF interval to be considered for enrollment. If preliminary eligibility is confirmed by the investigator, patients will then be scheduled for a Baseline Visit and will be required to return a valid set of Baseline diaries. Final eligibility will be determined at the Baseline Visit.

Patients will return to the study site for evaluation at scheduled visits at Weeks 2, 6, 12, 24, 36, and 52. Patients will be contacted by telephone before the start of each 3-day PD diary completion period to be reminded to complete the diary. A final Safety Follow-Up Visit (Week 56) will occur 28 ± 3 days after the patient’s last open-label dose of tozadenant. Upon starting study treatment, patients will receive open-label tozadenant at a dose of 120 mg BID. Adjustments to the open-label tozadenant dose are allowed to be made by the investigator starting at Week 2 and at any of the subsequent visits. Doses of 60 or 120 mg BID are permitted; the investigator may adjust a patient’s dose to either level as clinically indicated. The Interactive Response System (IXRS) will be used to assign, track and manage the tozadenant inventory at each study site.

The Schedule of Events/Evaluations for is shown below in [Table 1](#).

Table 1: Schedule of Events/Evaluations

Assessments	Study Period	Baseline	Open-Label Treatment						Safety	Early	Unscheduled
	Screening ^a	Predose	(52 weeks)						Follow-Up	Termination ^w	
	Study Week ^b	BL	2	6	12	24	36	52	56		
Study Visit	-6 to -1		(± 3 d)	(± 3 d)	(± 3 d)	(± 7 d)	(± 7 d)	(± 14 d) [16 weeks]	(28 ± 3 d after last dose of IMP)		
	V1	V2	V3	V4	V5	V6	V7	V8	V9		
Written Informed Consent	X										
Demographics and Medical History, including neurological and PD history	X										
Recording of concomitant and anti-PD medications	X	X	X	X	X	X	X	X	X	X	X

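### The Week 52 instructions tie the Safety Follow-Up window to Baseline, so completers could be checked 14 to 42 days off drug instead of 25 to 31

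*Protocol*

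**What the plan says.** **The last-dose rule.** Protocol 3.1 and SAP section 3 state: "A final Safety Follow-Up Visit (Week 56) will occur 28 ± 3 days after" the last open-label dose. The Visit 9 column header in Protocol Tables 1 and 4 and SAP Table 1 gives "28 ± 3 d after last dose of IMP". Protocol 6.1 places completers' visit at the "Safety Follow-Up Visit 28 ± 3 days after completion of the 52-week open-label treatment period". The synopsis says patients are assessed "regularly throughout the study and 4 weeks after their last dose of IMP".

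**The Baseline rule.** The scheduling step that a site carries out at Week 52, Protocol 6.2.18 item 15, reads: "Schedule the Safety Follow-Up Visit (Week 56). If needed, use the visit window in relation to the date of the Baseline visit". Footnote b of the same three tables reads: "Visit windows for scheduled visits after Baseline (V2) are in relation to the date of the Baseline Visit (V2". It makes no exception for Visit 9, and Protocol 6.1 counts Week 56 among the scheduled visits.

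**The section for the visit itself.** Protocol 6.2.19 does not settle the matter: "All patients who complete dosing and study evaluations through Week 52 will be scheduled for a required Safety Follow-Up Visit at Week 56". It gives neither an anchor date nor a window.

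**The concern.** Two instructions for one visit use different reference dates, and the one at the point of action is the wrong one. The last-dose rule is clearly what was intended; item 15 repeats a sentence that suits the earlier on-treatment visits. At Visit 9 the anchors can give different dates, because Visit 8 has the widest window of the treatment visits in Table 1 (± 14 days) and treatment stops there.

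Visit 9 is the only scheduled off-drug check for completers. It covers adverse-event questioning, laboratory tests, ECG, blood pressure and the C-SSRS. The SAP also counts treatment-emergent events up to the Safety Follow-Up (SAP 5.12), so its date fixes how much off-drug time contributes to the primary safety variable. It also affects what the Safety Follow-Up summaries in SAP 9.8 describe: readings at a fairly uniform four weeks off drug, or readings spread over a much wider interval. Patients who stop early are tied to the last dose without ambiguity (Protocol 3.1, 4.3.2 and 6.1), so completers could be observed over a different off-drug interval from theirs.

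**Working it through.** **Inputs**

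- Baseline is taken as Day 0, so Week 52 is 52 × 7 = Day 364 and Week 56 is 56 × 7 = Day 392.
- The Visit 8 window is ± 14 days (Table 1 header): Days 350 to 378, which is 29 possible days.
- L is the day of the last dose. **Assumption:** L is the Visit 8 day. Patients are reminded to take IMP that morning (6.2.17), 6.2.18 lists collection of IMP but no dispensing, and the last-dose date is entered on completion of Visit 8 (5.8).
- The width of a Baseline-anchored Visit 9 window, w, is **not stated**. It is shown below as a range.

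**Step 1: the plan's own figure.** On the nominal schedule, 392 − 364 = 28 days, and ± 3 gives 25 to 31 days off drug. The stated rule is reproduced.

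**Step 2: Visit 9 booked at Day 392.** Time off drug is 392 − L.

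- Latest Visit 8: 392 − 378 = 14 days.
- Earliest Visit 8: 392 − 350 = 42 days.
- Within 25 to 31 days only if L is between 392 − 31 = 361 and 392 − 25 = 367. That is 7 of the 29 permitted Visit 8 days.

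**Step 3: can one date satisfy both rules?** The last-dose rule allows L + 25 to L + 31. A Baseline window allows 392 − w to 392 + w. They overlap when L + 25 ≤ 392 + w and L + 31 ≥ 392 − w, that is, when |L − 364| ≤ 3 + w. A site using only the Baseline window would see patients from (392 − w) − 378 to (392 + w) − 350 days off drug.

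| Assumed w (days) | Days off drug, Baseline window only | Distance of last dose from Day 364 at which no date meets both rules |
|---|---|---|
| 0 | 14 to 42 | 4 to 14 days |
| ± 3 | 11 to 45 | 7 to 14 days |
| ± 7 | 7 to 49 | 11 to 14 days |
| ± 14 | 0 to 56 | none; a shared date always exists |

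The ± 7 and ± 14 rows only bound the unknown width; no text supports them for Visit 9.

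**Step 4: under the last-dose anchor.** A last dose on Day 350 puts Visit 9 at Days 375 to 381. A last dose on Day 378 puts it at Days 403 to 409. Every completer is then due 25 to 31 days off drug.

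**The case against.** The strongest reply is that the documents already settle the timing. The last-dose rule appears in every Visit 9 header and in several sections, and 3.1 attaches the label Week 56 to it, so the same label in 6.2.18 and 6.2.19 can be read that way. Item 15 is conditional, and the only window given for Visit 9 is the one in the header. A specific header should also prevail over a general footnote. Day 392 is not in the documents; it is simply Week 56 counted from Baseline. The figures of 14 and 42 days need both a site that sets the header aside and a Visit 8 at the very edge of its window.

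Much of this stands. The intended rule is not in doubt, the extremes are extremes, and a careful site would get it right. It does not remove the problem, because item 15 names Baseline as the reference date in the step the site follows. A site could obey item 15 and still breach the 28 ± 3 day rule. With about 120 sites, a uniform reading should not be relied on.

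The reply also narrows the harm, partly rightly. Serious events must be reported for 4 weeks after the last IMP whatever the date of Visit 9 (9.2.2). A late Visit 9 still asks about events since the previous visit. The analysis is single-arm and descriptive, so no treatment comparison is biased. The follow-up of adverse events described in 9.1.4, usually 30 days after stopping, concerns events already known; it does not replace a scheduled check for new ones. What an early visit can lose is new non-serious events and laboratory or ECG changes that arise after it. A late visit can miss transient changes that have already resolved.

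**Conclusion.** The concern holds. For completers, 6.2.18 item 15 and footnote b anchor Visit 9 to Baseline, contrary to the rule of 28 ± 3 days after the last dose, and 6.2.19 does not resolve the conflict. A site booking at Day 392 would check patients 14 to 42 days off drug instead of 25 to 31. This rests on the last dose being taken on the Week 52 visit day and, for other window widths, on the assumed w. There is no discrepancy when Visit 8 falls on Day 364, and Day 392 remains compliant for a Visit 8 within 3 days of it. The number of patients affected cannot be estimated, because the documents do not say how often Visit 8 departs from Day 364 or which instruction sites would follow. This is a correctable conflict in an operative instruction; it does not invalidate the trial, but it should be fixed.

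**What to change.** 1. In Protocol 6.2.18 item 15, replace the Baseline sentence with: *Schedule 28 ± 3 days after the last dose of IMP.* This is the essential change.
2. In Protocol 6.2.19, use the same wording in place of the bare reference to Week 56.
3. In footnote b of Protocol Tables 1 and 4, add an exception for Visit 9. Make the same edit in SAP Table 1 so that the schedules agree; sites do not book from the SAP, so this one is for consistency.

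The cost is two protocol sentences and one footnote exception repeated in three tables. Sites already record the last-dose date on completion of Visit 8 (5.8), so no new data, visits or analyses are required.
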